9.2.1. Inclusion Criteria

Patients must meet all of the following inclusion criteria to be eligible for inclusion in the study:

Objective 1 Inclusion Criteria:

- Enrolled in the CorEvitas RA Registry and initiated tofacitinib on or after November 2012.
- Initiate tofacitinib (defined as first ever use of tofacitinib) at Registry enrollment visit or at a Registry follow-up visit after November 2012.
- Have prior use of rituximab.
- Have Clinical Disease Activity Index (CDAI) measured at baseline.

Objective 2 Inclusion Criteria:

- Enrolled in the CorEvitas RA Registry and initiated tofacitinib on or after November 2012.

- Initiate tofacitinib (defined as first ever use of tofacitinib) at Registry enrollment visit or at a Registry follow-up, after November 2012.
- Have prior use of rituximab.
- Have CDAI measured at baseline and appropriate follow-up visit.
- Have any of the following:
 - a. A 6-month follow-up visit with persistent use of tofacitinib.
 - b. A 6-month follow-up visit with a tofacitinib discontinuation occurring prior to the 6-month visit, with no new biologic systemic drug used prior to the 6-month study visit.
 - c. A study visit at or prior to the 6-month window with a tofacitinib discontinuation occurring at the study visit.
 - d. (Sensitivity analysis only) Any tofacitinib discontinuation prior to the 6-month study window.

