9.4. Data Sources

The CorEvitas RA Registry is an observational registry and therefore collects patient and physician data at patient clinical visits with the rheumatologist. Unlike clinical studies, visits are not timed at exact uniform time periods. Thus, time period definitions for the current study need to accommodate this unique feature of observational registries.

“Index visit” is defined as the visit when tofacitinib was initiated, ie, first ever use of tofacitinib. Only initiations at or after enrollment into the Registry are included.

A “6-month” follow-up is defined as a clinical visit to the rheumatologist 3 to 9 months from the enrollment visit in accordance with the Registry protocol.

Initiations between visits

If tofacitinib is initiated between visits, then baseline variables from the visit prior to the initiation of tofacitinib will be used, as long as the prior visit occurred within four months of the tofacitinib start date. Initiations that occur between visits and where the prior visit is greater than 4 months from the initiation will be excluded.

Multiple visits in the same time window

Given the observational nature of the data, it is possible for patients to have more than one visit that falls within a given follow-up period's allowed time window. For example, a patient might have a visit with outcomes collected at 5 months and then 9 months, both of which would qualify as a "6-month" visit. In that case, the latest visit will be chosen as the "6-month" follow-up since we would like to consider the longest follow-up possible. The exception to this rule is if values for the primary outcome are unavailable for the latest visit, in which case the first visit will be used instead.

Discontinuations prior to follow-up

For patients who discontinued tofacitinib prior to follow-up and who do not switch to another drug, the clinical or patient-reported outcome value at the follow-up visit will be used. If a patient discontinues and switches to another biologic/tsDMARD, the value at the switch visit, if available, will be used; otherwise, the value will be set to missing.

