4.4.3. Time Period Definitions

The CorEvitas RA Registry is an observational registry and therefore collects patient and physician data at patient clinical visits with the rheumatologist. Unlike clinical studies, visits are not timed at exact uniform time periods. Thus, time period definitions for the current study need to accommodate this unique feature of observational registries.

“Index visit” is defined as the visit when tofacitinib was initiated, i.e. first ever use of tofacitinib. Only initiations at or after enrollment into the Registry are included.

A “6-month” follow-up is defined as a clinical visit to the rheumatologist 3 to 9 months from the enrollment visit in accordance with the Registry protocol.

4.4.3.1. *Initiations between visits*

If tofacitinib is initiated between visits, then baseline variables from the visit prior to the initiation of tofacitinib will be used, as long as the prior visit occurred within four months of the tofacitinib start date. Initiations that occur between visits and where the prior visit is greater than 4 months from the initiation will be excluded.

4.4.3.2. *Multiple visits in the same time window*

Given the observational nature of the data, it is possible for patients to have more than one visit that falls within a given follow-up period’s allowed time window. For example, a patient might have a visit with outcomes collected at 5 months and then 9 months, both of which would qualify as a “6-month” visit. In that case, the latest visit will be chosen as the “6-month” follow-up since we would like to consider the longest follow-up possible. The exception to this rule is if values for the primary outcome are unavailable for the latest visit, in which case the first visit will be used instead.

4.4.3.3. *Discontinuations prior to follow-up*

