For patients who discontinue tofacitinib prior to 6 months window, the clinical or patient-reported outcome (listed in Section 4.4.5.2) will be imputed via last observation carried forward (LOCF), using only registry visits that occur before the discontinuation. Specifically, outcomes observed at a registry visit in the 6-month window will use data collected at that visit with the following exception. Patients that discontinue tofacitinib at a registry visit prior to the six month window will have the outcomes collected at that registry visit carried forward as the outcomes in the 6-month window. A patient that discontinues tofacitinib between registry visits will have the outcomes collected at the registry visit prior to the discontinuation carried forward as the 6-month outcome.

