4.4.6.6. Medications

- Previous drug therapies
 - Number of prior csDMARDs, (incl: MTX, Arava, Azulfidine, Plaquenil, Cyclosporine, Imuran, Minocin, Cuprimine, Ridaura)
 - Number of prior bDMARDs/JAKis (incl: TNFi: Enbrel, Humira, Remicade, Cimzia, Simponi; non-TNFi: Orencia, Actemra, Rituxan, Kineret, Kevzara; JAKis: Olumiant, Rinvoq)
 - History of prednisone use
- Line of therapy at tofacitinib initiation:
 - Number (%) with 2 prior biologics (I.e., RTX + 1 other biologic)
 - Number (%) with 3 prior biologics (I.e., RTX + 2 other biologics)
 - Number (%) with 4+ prior biologics (I.e., RTX + 3+ biologics)
- Concomitant therapies
 - Concomitant medications (none, MTX only, nonMTX csDMARD only, MTX & nonMTX csDMARD)
 - Current prednisone use
 - Prednisone dose, among current users
- Detailed description of RTX use:
 - Number (%) using RTX directly before tofacitinib
 - Duration of prior RTX use, where available
 - Line of therapy of RTX
 - Year of RTX discontinuation
- Total number (%) of discontinuations
- Reason for Discontinuation of RTX (among those who discontinue

RTX at or after enrollment in registry)

- Number of patients with at least 1 reason reported
- Total number of reasons
- %Safety, %Efficacy, %Cost/Insurance, %Other reasons
- Tofacitinib initiation year

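### The SAP's carry-forward rule omits a stop and switch at a visit inside the 6-month window, so a value on the successor drug can become the tofacitinib outcome

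*Protocol*

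**What the plan says.** Eligibility for Objective 2 is in Protocol 9.2.1.

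- Criterion (b) admits a patient who stopped before the 6-month visit, "with no new biologic systemic drug used prior to the 6-month study visit".
- Criterion (c) admits a patient through "A study visit at or prior to the 6-month window with a tofacitinib discontinuation occurring at the study visit".
- Every patient must also meet this condition: "Have CDAI measured at baseline and appropriate follow-up visit".

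The value to be analysed is set elsewhere, and the two documents differ.

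- Protocol 9.4 gives the follow-up value to one group only: "For patients who discontinued tofacitinib prior to follow-up and who do not switch to another drug". For the others, "If a patient discontinues and switches to another biologic/tsDMARD, the value at the switch visit, if available, will be used"; if there is none, the outcome is missing.
- SAP 4.4.3.3 carries the last observation forward for patients who stop before the window, "using only registry visits that occur before the discontinuation". It then specifies a stop at a visit before the window (that visit's value is carried forward) and a stop between visits (the preceding visit's value). Otherwise an in-window visit supplies its own data.
- SAP 4.4.3.2 says that with several visits in the window "the latest visit will be chosen as the" 6-month follow-up. Its example is a patient seen at 5 and 9 months.

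SAP 4.4.6.6 names JAK inhibitors as a group of their own within prior therapies ("JAKis: Olumiant, Rinvoq").

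**The concern.** Aim 2 reports change in CDAI and the proportion achieving the MCID as outcomes of tofacitinib initiators. If the chosen 6-month value was recorded after the patient had moved to another biologic or tsDMARD, part of the reported change belongs to that drug. Where the successor works, the error makes the result look better, which is the direction both documents say they anticipate.

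The two documents also give different values for the same patient, so the primary Aim 2 outcome is not fully defined for in-window switchers.

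**Working it through.** The plan states no figure on this point, so the check sets the rules against each way a patient can stop and switch. SAP 4.4.3.3's sentence on stops between visits is read as applying whether the stop falls before or inside the window, since it sets no time limit.

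| Stop and switch | Protocol 9.4 | SAP 4.4.3 | Post-switch value used? |
|---|---|---|---|
| Between visits, later visit in window | Switch-visit value, else missing | Visit before the stop | No |
| At a visit before the window | That visit's value | That visit's value | No |
| At a visit inside the window, second visit in window | Switch-visit value | Neither specified case applies; latest visit chosen | Yes, under the SAP |

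In the third row, take the SAP's own example. A patient stops and switches at month 5 and is seen again at month 9. Both visits are in the window, the stop is not before the window, and it is not between visits. The month 9 value is used, after up to 9 − 5 = 4 months on the new drug. Under Protocol 9.4 the month 5 value would be used.

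The wording of criterion (b) does not determine this. A patient who switches to a true biologic at month 5 can enter through criterion (c), and SAP 4.4.3.2 then selects month 9 in the same way. The SAP does not tie the choice of value to the criterion through which the patient qualified.

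Size. Inputs:

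- n = about 107 patients with CDAI at baseline and 6 months (Protocol 9.5 and SAP 4.4.9, 31 March 2021 data cut);
- k = number of exposed patients, not given, assumed 1 to 3;
- d = CDAI difference between the post-switch value and the switch-visit value, not given, assumed 5 to 10 points.

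Shift in mean change = k × d / n.

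- Low: 1 × 5 / 107 = 0.05 points.
- High: 3 × 10 / 107 = 0.28 points.

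For the MCID proportion, each patient counts for 1/107 = 0.9 percentage points. Three patients give at most 3/107 = 2.8 points, and only if all three change from non-achiever to achiever. That is an upper limit: a difference of 5 to 10 points does not by itself exceed the 12-point threshold for patients with high activity at index.

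**The case against.** The strongest reply is that eligibility and value selection are separate, and that the value rules already keep the successor drug out in most cases. Protocol 9.4 names tsDMARDs, so a move to another JAK inhibitor takes the switch-visit value or is missing. If it is missing, the patient also appears to fail the requirement for a follow-up CDAI. The SAP's carry-forward does not depend on what drug follows. This stands for the first two rows of the table.

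The term in criterion (b) may also have been meant broadly. In SAP Table 1, footnote 5 calls csDMARDs non-biologic systemic therapy, and footnote 6 speaks of the current biologic in a cohort where everyone starts tofacitinib. This is fair evidence of loose terminology rather than a deliberate gap, though it also shows that the term needs defining.

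A reader might infer that criterion (b) lets JAK-inhibitor switchers stay in Objective 2 and that their response to the new drug is generally credited to tofacitinib. The documents do not support that, for the reasons above.

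Criterion (c) could also be taken to imply that the stop visit supplies the outcome. The SAP does not say so, and its latest-visit rule points the other way. Protocol 9.7 allows the SAP to modify the protocol's plans, so the switch-visit rule in Protocol 9.4 cannot be relied on to override the SAP. The third row therefore remains.

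**Conclusion.** The point holds in a narrow form. Under the current SAP, a patient who stops tofacitinib and starts another biologic or tsDMARD at an in-window visit, and has a later in-window visit, contributes a post-switch value; Protocol 9.4 would not use it. The cause is the limited scope of SAP 4.4.3.3 combined with the latest-visit rule, and it affects biologic and JAK-inhibitor switchers alike. The mismatch between criterion (b) and Protocol 9.4 is real but secondary.

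The effect is probably small: about 0.05 to 0.3 CDAI points on the mean change. This rests on the assumed 1 to 3 exposed patients, the assumed 5 to 10 point difference, and the 2021 count of about 107, which will differ at the final data cut. The direction is also an assumption, since the documents give no data on response after a switch. It is worth correcting because the stated rule gives a wrong value for these patients and the two documents disagree, not because it threatens the descriptive conclusions.

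**What to change.** 1. In SAP 4.4.3.2 and 4.4.3.3, state that no value recorded after the start of a new biologic or tsDMARD, including another JAK inhibitor, is used as the 6-month outcome, and that this takes precedence over the latest-visit rule.
2. In SAP 4.4.3.3, state that for a stop at a visit inside the window the value at that visit is used. This also reaches patients who stop without switching, for whom Protocol 9.4 uses the follow-up value, so the two texts must be settled together.
3. In Protocol 9.2.1(b), use the same biologic/tsDMARD term as Protocol 9.4.
4. Reconcile Protocol 9.4 with SAP 4.4.3.3, and update the limitations text in SAP 4.5.2 (and its counterpart in Protocol 9.9), which still describes follow-up values for stoppers and switch values for switchers.
5. Report the number of patients who stopped and switched at an in-window visit and had a second in-window visit.

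The cost is a few sentences in each document and one extra count. No new data are needed, and only the in-window stoppers with a later in-window visit change value.

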8.2.1. Hypotheses

This study is descriptive with no formal hypothesis, but it is anticipated that outcomes will improve over the 6-month time period.

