9.4.2. Study Outcomes

Objective 1: Characterize Patients at tofacitinib initiation

Primary Outcome:

- Objective 1 is to characterize patients at tofacitinib initiation. All variables as outlined in the SAP will be summarized for this aim.

Objective: Describe change in 6-month outcomes.

Primary Outcome:

- Change in CDAI.

Secondary Outcomes:

- Achievement of Minimum Clinically Important Difference (MCID):² (change in CDAI from baseline to follow-up = Δ CDAI).

CDAI at Index	MCID to Define Improvement in Disease Activity at FU Visit If ΔCDAI>MCID
Low: CDAI \leq 10	1
Moderate: 10 $>$ CDAI \leq 22	6
High $>$ 22	12

- Change in HAQ.
- Change in patient pain.
- Change in patient fatigue.
- Number (%) of tofacitinib discontinuations prior to or at 6-month visit.

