9.9. Limitations of the Research Methods

The CorEvitas RA Registry used in this research includes a sample of adults with RA that are not necessarily representative of all adults with RA in the US, or of those in emerging markets outside the United States (US). In particular, these are patients with RA with clinical visits with rheumatologists.

Most importantly for this study, in the US rituximab is typically prescribed as a later line therapy, after failure of one or more tumor necrosis factor inhibitor (TNFi). It is also given as a first-line bDMARD to patients with contraindications to tumor necrosis factor (TNF) inhibitors (eg, interstitial lung disease).⁴ This may differ from prescribing patterns in countries other than the US, which could influence the generalizability of the results to RA patients outside of the US.

In addition, history of medication use prior to enrollment is derived from what is reported by patients and their current rheumatologist within the registry. Since the registry is not based on an inception cohort, patients may not be able to recall their entire medication history, leading to possible mischaracterization regarding prior use of rituximab. The registry captures physician-reported prescribing, but there are no measures of patient adherence.

Confounding by indication can occur when factors that determine physicians' selection of a particular treatment (eg, disease severity, comorbidities) also affect the outcome being studied. There are certain conditions (tuberculosis [TB], lymphoma) that would prompt the prescribing of rituximab. This population could have different outcomes than a population without these comorbidity histories.

Patients who maintain treatment at 6 months may have different outcomes compared to the outcomes those who discontinue or switch would have had, had they not discontinued/switched. This study takes steps to mitigate this potential bias by including values at follow-up for those who discontinue treatment and values at switch for those who switch, as described above.

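### Protocol 9.2.1 leaves patients who stop tofacitinib between visits and start a new biologic out of the main Objective 2 set, while the SAP can keep them, so the primary CDAI outcome has two different analysis sets

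*Protocol*

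**What the plan says.** Protocol 9.2.1 requires CDAI at baseline and at a suitable follow-up visit for Objective 2, plus one of four routes:

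- (a) "A 6-month follow-up visit with persistent use of tofacitinib".
- (b) A 6-month visit after an earlier stop, but only "with no new biologic systemic drug used prior to the 6-month study visit".
- (c) A stop that takes place at a study visit, in or before the 6-month window.
- (d) "Sensitivity analysis only) Any tofacitinib discontinuation prior to the 6-month study window".

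For a patient who stops and switches, Protocol 9.4 says that "the value at the switch visit, if available, will be used; otherwise, the value will be set to missing". Protocol 9.4.2 lists as a secondary outcome "Number (%) of tofacitinib discontinuations prior to or at 6-month visit", without a denominator. Protocol 9.9 says that bias from stopping is mitigated by "including values at follow-up for those who discontinue treatment and values at switch for those who switch"; SAP 4.5.2 repeats the sentence.

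The SAP differs. Section 4.4.2 takes Aim 1 patients who have a 6-month visit with outcomes and is silent on new biologics. Section 4.4.3.3 states: "A patient that discontinues tofacitinib between registry visits will have the outcomes collected at the registry visit prior to the discontinuation carried forward". That value then stands in for the 6-month result, with no exception for switchers. SAP 4.4.7.2 contains no sensitivity analysis for Aim 2; the SAP's amendment log records its removal on 06-Jan-2023.

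**The concern.** The secondary objective is to describe 6-month outcomes in tofacitinib initiators with prior rituximab. Under Protocol 9.2.1, entry to the main set depends partly on what happens after initiation: whether the drug was stopped, whether the stop fell on a visit, and whether another biologic followed. If the patients left out did worse than those kept, mean CDAI improvement and the MCID percentage are overstated. If the discontinuation percentage uses the Objective 2 set as its denominator, known discontinuations are missing from both its numerator and its denominator.

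The SAP does not settle the matter. Protocol 9.7 allows the SAP to modify the plan but expects major changes to primary endpoint definitions or analyses to appear in a protocol amendment. Protocol v3.0, dated 13 January 2023, came a week after the SAP's carry-forward rule. Its amendment entries of that date concern Sections 9.1 and 3 only, so 9.2.1 and 9.4 kept the other rule. The SAP was amended again on 04-May-2023 and kept carry-forward. Two analysts could each follow a current document and report a different N and a different CDAI change.

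**Working it through.** **The plan's own figures.** No power calculation exists to reproduce ("This study is descriptive with no formal hypothesis"). The line-of-therapy split in Protocol 9.5 is consistent: 8 + 365 = 373, 8/373 = 2.1% and 365/373 = 97.9%. The ~107 patients with both CDAI values is a registry count and cannot be re-derived. It is 107/376 = 28.5% of those with baseline CDAI. The other 376 - 107 = 269 lack a 6-month value for reasons not given.

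**Tracing the patient.** Take a patient who stops between visits and has started a new biologic before the 6-month visit.

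| Rule | Result |
|---|---|
| Protocol 9.2.1 (a) | Fails: use is not persistent |
| Protocol 9.2.1 (b) | Fails: a new biologic was used |
| Protocol 9.2.1 (c) | Fails: the stop was not at a visit |
| Protocol 9.2.1 (d) | Sensitivity only, and only if the stop came before the window; a stop within months 3 to 9 has no route |
| Protocol 9.4 | Missing, unless a switch-visit value exists |
| SAP 4.4.2 | Included if there is a 6-month visit with outcomes |
| SAP 4.4.3.3 | Last pre-stop visit carried forward; if that is the index visit, CDAI change = 0 and MCID is not met |

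**Discontinuation, taken alone.** With d stoppers among n included and k known stoppers left out, (d + k)/(n + k) - d/n = k(n - d)/[n(n + k)]. This is positive whenever d < n, so this exclusion on its own lowers the percentage.

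**Illustration of size.** Everything except 107 is assumed: k = 5 to 30; retained patients with mean CDAI change -8, MCID 40% and discontinuation 20%; each left-out patient scored as change 0, MCID not met, discontinued. If the k patients lie within the 107:

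- mean = -8 × (107 - k)/107
- MCID = 40% × (107 - k)/107
- discontinuation = [0.20 × (107 - k) + k]/107

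If they come on top of the 107, the formulas become -8 × 107/(107 + k), 40% × 107/(107 + k) and (0.20 × 107 + k)/(107 + k).

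| k | Within 107: mean / MCID / discontinued | On top of 107: mean / MCID / discontinued |
|---|---|---|
| 5 | -7.63 / 38.1% / 23.7% | -7.64 / 38.2% / 23.6% |
| 10 | -7.25 / 36.3% / 27.5% | -7.32 / 36.6% / 26.8% |
| 20 | -6.50 / 32.5% / 35.0% | -6.74 / 33.7% / 32.6% |
| 30 | -5.76 / 28.8% / 42.4% | -6.25 / 31.2% / 37.5% |

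More generally, with a mean change of s in the left-out patients and -8 in the rest, including them moves the mean by (k/107)(s + 8). At k = 10 and s = 0 this is 0.75. At s = -8 it is zero, and below -8 it changes sign.

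**The case against.** The strongest reply is that the current SAP already handles these patients: it has no bar on new biologics, it carries a value forward, it is the later document, and Protocol 9.7 lets it modify the plan. That stands to this extent: exclusion is settled only if 9.2.1 governs. It does not remove the conflict, because no protocol amendment carries the change for the primary outcome. SAP 4.4.2 also still asks for a 6-month visit, so switchers without one are lost under either document.

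The condition in (b) has a sensible purpose, which is to keep a CDAI measured on another biologic from being credited to tofacitinib. The fix must preserve that.

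Three stronger inferences are tempting and not supported:

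- **That the excluded patients are clear treatment failures.** The documents give no reasons for stopping tofacitinib. The codes listed for stopping rituximab include side effects, insurance and patient preference as well as efficacy.
- **That the discontinuation percentage is certainly understated.** Its denominator is not stated. Selection also runs the other way: (c) can admit early stoppers with no 6-month visit, while (a) requires that visit of patients still on drug. The net direction is unknown.
- **That every such switcher is excluded.** If the latest in-window visit lacks CDAI, Protocol 9.4 falls back to the first, at which the patient may still have been on tofacitinib. Criterion (b) names a biologic, whereas 9.4 also names tsDMARDs, so a move to another JAK inhibitor is not clearly barred.

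The sentence in Protocol 9.9 is not simply untrue either, since it refers back to 9.4, which admits that some values will be missing. What stands is that it does not reach patients with no switch-visit value. In the SAP, the same sentence no longer matches the carry-forward rule.

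**Conclusion.** The point holds as an unreconciled conflict over who is in the Aim 2 set for CDAI change, with a selection problem if Protocol 9.2.1 governs. Bias in CDAI and MCID is conditional on the left-out patients having done worse. Loss from the discontinuation count is conditional on its denominator being the Objective 2 set. The size cannot be found from the documents. In the illustration with these patients inside the 107, the mean change and MCID rate shrink by k/107, from 4.7% at k = 5 to 28.0% at k = 30. Those figures rest on assumed counts and on scoring every such patient as no change; they are not estimates. The matter should be corrected before results are reported, because a descriptive study depends on saying exactly whom it describes.

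**What to change.** Amend the protocol so that 9.2.1, 9.4 and 9.9 agree with SAP 4.4.2, 4.4.3.3 and 4.5.2 on one rule:

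1. In 9.2.1 (b), delete the condition on a new biologic. In both documents, do not require a 6-month visit or 6-month CDAI for patients known to have stopped earlier. Delete (d), or restore its analysis in the SAP.
2. For CDAI change, MCID and the patient-reported outcomes, use the last post-baseline visit on tofacitinib, in line with SAP 4.4.3.3, and never a value measured on the new drug. Say explicitly that the index visit is not carried forward. Where no post-baseline on-drug visit exists, leave the change missing and print the number of such patients beside the CDAI result in Tables 3 and 4. Replace the switch-visit rule in Protocol 9.4 accordingly.
3. Show MCID with these patients counted as non-achievers as a sensitivity row. Making that the main row would let one patient show a qualifying CDAI improvement in one line and non-response in the next.
4. State the discontinuation denominator, count every known between-visit switcher in its numerator and denominator, and add a discontinuation row to Table 3, which has none.
5. Rewrite the mitigation sentence in Protocol 9.9 and SAP 4.5.2 to describe the adopted rule.

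The cost is a protocol amendment, a SAP update and some reprogramming; the data are already in the Registry. The price in reporting is probably slightly less favourable figures, and Ns that differ between rows.
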